22.7 EXPLORATORY ENDPOINTS

Exploratory endpoints will be described in the SAP and will include:

- Reduction in aberrant and abnormal IELs by flow cytometry, immunohistochemistry and TcR clonality analyses (including % patients with normalization in IELs)
- PGA and PtGA
- Quality of Life Assessments:
 - SF-12 v. 2
 - EQ-5D
- Biomarkers of disease activity
- PK, PD, and PK/PD correlations
- CeD PRO

The exploratory variables will be tabulated by treatment group and time point (if feasible) using the ITT or PP populations as appropriate.

The exploratory variable CeD PRO will be analyzed using the same method as for the GSRS and CeD-GSRS.

Pharmacokinetics of AMG 714 in RCD-II patients will also be characterized using nonlinear mixed-effects modeling, including evaluation of effects of major covariates (e.g., weight or BMI, BSA, sex, biochemical parameters and disease characteristics at baseline) on AMG 714 exposure.

For PK/PD correlations, individual patients' exposure measures obtained from the PK analysis will be graphically assessed with select PD endpoints and if associations are observed will be further elucidated with modeling and/or summaries by quartiles of exposure.

Exploratory exposure-response analysis will be performed for efficacy, safety, and biomarker measures. These exploratory analyses will be assessed with appropriate descriptive statistics and graphical displays.

Change from baseline (by time point) will also be presented for reduction in aberrant IELs by immunochemistry and TcR clonality analyses, PGA and quality of life assessments (SF-12 v. 2 and EQ-5D).

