8.2.1 Definition of derived variables

Geometric mean will be calculated as:

$$\text{mean}_{\text{geo}} = \exp\left\{\frac{1}{n} \sum_{i=1}^n \ln x_i\right\}.$$

Values that are missing or not available will be ignored in calculation of geometric mean.

CV%_{geo} will be calculated using the following formula:

$$\text{CV}\%_{\text{geo}} = 100\% \cdot \sqrt{\exp V_{\ln} - 1}.$$

Values that are missing or not available will be ignored in calculation of CV%_{geo}.

Absolute change from baseline for a given treatment needs to be calculated, the following formula will be used:

$$\text{Absolute change from baseline} = \text{Post-baseline value} - \text{Pre-dose value}.$$

For weekly scores, Week 0 score is considered to be the baseline value. If Week 0 score is not available, the first non-missing result within 2 weeks of treatment will be used as baseline. For daily scores (e.g. CeD PRO), Day 0 score is considered to be the baseline; in case Day 0 score is not available, the first non-missing result within 2 weeks of treatment will be used as baseline. Otherwise, the given subject will be considered non-evaluable for the specific test. In case pre-dose value doesn't exist (i.e. for biopsy endpoints), screening value will be used as baseline.

In the case where relative (%) change from baseline needs to be calculated, the following formula will be used:

$$\text{Relative (\%) change from baseline} = (\text{Post-baseline value} - \text{Pre-dose value}) / (\text{Pre-dose value}) \cdot 100\%.$$

For weekly scores, Week 0 score is considered to be the baseline value. If Week 0 score is not available, the first non-missing result within 2 weeks of treatment will be used as baseline. For daily scores (e.g. CeD PRO), Day 0 score is considered to be the baseline; in case Day 0 score is not available, the first non-missing result within 2 weeks of treatment will be used as baseline. Otherwise, the given subject will be considered non-evaluable for the specific test. In case pre-dose value doesn't exist (i.e. for biopsy endpoints), screening value will be used as baseline.

Body mass index (BMI) is calculated using the formula:

$$\text{BMI (kg/m}^2\text{)} = \text{weight (kg)} / [\text{height (m)} * \text{height (m)}].$$

Body surface area (BSA) is calculated using Dubois' formula:

$$\text{BSA (m}^2\text{)} = 0.007184 * \text{height (cm)}^{0.725} * \text{weight (kg)}^{0.425}.$$

Table 2 Decimal places for summary statistics of continuous and categorical variables

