β is the parameter estimate of the baseline total CeD PRO score,

γ is the parameter estimate of day,

λ_{jk} is the fixed interaction effect due to treatment j and day k ,

η_i is the random effect due to subject i ,

ε_{ijk} is the random error for subject i from treatment group j for day k .

Note that the proper functional form of the time (day) will be explored, e.g. square of day might be added.

The following SAS program will be used for carrying out the daily level analysis:

```
proc glimmix data=cedpro_d;
  class subjid trt;
  model cedpro_d = cedpro_d_bl trt day trt*day / solution;
  random _residual_ / subject=subjid type=AR(1);
```

```
estimate "AMG 714 vs Placebo" trt 1 -1 /alpha=0.05 cl;  
lsmeans trt /alpha=0.05 cl;  
ods output CovParms=Cov_Par LSMeans=LS_est Estimates=Eff_est  
FitStatistics=Fit_Stat ParameterEstimates=Par_est  
Tests3=Type_3;  
  
run;
```

For the weekly level data, the following model will be fitted:

$$Y_{ijk} = \mu + \alpha_j + \gamma_k + \lambda_{jk} + \beta \cdot \text{baseline CeD PRO}_{ij} + \eta_i + \varepsilon_{ijk},$$

where

Y_{ijk} is the total CeD PRO score for subject i ($i = 1, \dots, n_j$) from treatment group j ($j = 1, 2$) at week k ($k = 0, 1, \dots, 16$),

μ is the overall mean,

α_j is the fixed effect due to treatment j ,

γ_k is the fixed effect due to week k ,

λ_{jk} is the fixed interaction effect due to treatment j and week k ,

β is the parameter estimate of the baseline total CeD PRO score,

η_i is the random effect due to subject i ,

ε_{ijk} is the random error for subject i from treatment group j for week k .

The following SAS program will be used for carrying out the weekly level analysis:

```
proc glimmix data=cedpro_w;  
class subjid trt week (ref=FIRST);  
model cedpro_w = cedpro_w_bl trt week trt*week / solution;  
random _residual_ / subject=subjid type=AR(1);  
estimate "AMG 714 vs Placebo" trt 1 -1 /alpha=0.05 cl;  
estimate "Week 0: AMG 714 vs Placebo" trt 1 -1  
trt*week 0 0 0 0 0 0 0 0 0 0 0 0 0 0 0 0 0 1  
0 0 0 0 0 0 0 0 0 0 0 0 0 0 0 0 0 -1 /alpha=0.05 cl;  
estimate "Week 1: AMG 714 vs Placebo" trt 1 -1  
trt*week 1 0 0 0 0 0 0 0 0 0 0 0 0 0 0 0 0 0  
-1 0 0 0 0 0 0 0 0 0 0 0 0 0 0 0 0 0 /alpha=0.05 cl;  
...  
estimate "Week 16: AMG 714 vs Placebo" trt 1 -1  
trt*week 0 0 0 0 0 0 0 0 0 0 0 0 0 0 0 0 1 0  
0 0 0 0 0 0 0 0 0 0 0 0 0 0 0 0 -1 0 /alpha=0.05 cl;  
lsmeans trt /alpha=0.05 cl;  
lsmeans trt*week /alpha=0.05 cl;  

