ods output CovParms=Cov_Par LSMeans=LS_est Estimates=Eff_est  
FitStatistics=Fit_Stat ParameterEstimates=Par_est  
Tests3=Type_3;  
  
run;
```

Due to the repeated structure of the data, the measurements within a subject will be correlated. Therefore, it is assumed that the overall covariance matrix of the response is block-diagonal (e.g. the observations between different subjects are not related, but the same correlation structure exists within subjects). In order to determine the covariance structure that best fits the data, the same model with different covariance structures is fitted. Initially, the models will be fitted assuming first-order autoregressive (AR(1)) variance-

covariance structure. Common within and between treatment variance components (compound symmetry (CS), and Toeplitz covariance structures) will be further explored to increase sensitivity of statistical tests. The best model will be chosen by comparing the Akaike Information Criterion (AIC) of the models with different covariance structures.

Note that the value of `type` will be changed according to which covariance structure is being fitted.

The modelling results (parameter estimates, covariance parameter estimates, estimated treatment effect, marginal means estimates and results of the check of assumptions) will be tabulated and 95% confidence intervals added, where appropriate. If the parametric assumptions are not met, then in addition to the above-specified model, a generalized estimating equation (GEE) approach will be used as well.

The baseline and post-baseline weekly total CeD PRO scores along with the change from baseline values will also be described by summary statistics and tabulated by treatment group. Change from baseline for the weekly CeD PRO scores of individual questions (calculated as the average score of a question within a week) will also be tabulated by week and treatment group and described by summary statistics. The scores of individual questions and the total daily CeD PRO scores will be listed, as well as the total and by question weekly CeD PRO scores. Mean curves of both the total weekly and daily CeD PRO scores as well as the individual questions will also be plotted by time point and treatment group.

A tabulation of the proportion of subjects with at least a 50% change from baseline for ≥ 6 weeks will be provided. This analysis will be done internally by Celimmune.

ITT population will be used for summarizing CeD PRO results.

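### The weekly CeD PRO model uses Week 0 as both baseline covariate and response, which shrinks the overall treatment estimate by up to 1/17 (5.9%)

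*SAP*

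**What the plan says.** SAP 8.7.6 fits the weekly CeD PRO score with the statement "model cedpro_w = cedpro_w_bl trt week trt*week / solution". The accompanying text lets the week index run from 0 to 16, and the first week-specific contrast in the code is "Week 0: AMG 714 vs Placebo". An overall treatment contrast is requested as `trt 1 -1`, with no interaction coefficients.

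SAP 8.2.1 fixes the baseline: "For weekly scores, Week 0 score is considered to be the baseline value". For daily data it says "For daily scores (e.g. CeD PRO), Day 0 score is considered to be the baseline". The code keeps the two apart, with `cedpro_w_bl` in the weekly model and `cedpro_d_bl` in the daily one. If Week 0 is missing, the first available result within two weeks of treatment becomes the baseline.

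The GSRS model in SAP 8.6.2 also adjusts for baseline, but its response weeks start at 1. Protocol 22.7 says: "The exploratory variable CeD PRO will be analyzed using the same method as for the GSRS and CeD-GSRS".

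SAP 8.7.6 also plans "A tabulation of the proportion of subjects with at least a 50% change from baseline" lasting at least six weeks. It gives no direction, although a lower score means milder symptoms.

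**The concern.** A baseline-adjusted comparison of the arms at baseline cannot show what treatment does. Printed next to the contrasts for Weeks 1 to 16, it invites a reader to treat it as one of them. It also feeds a value close to zero into the overall estimate, which is the single-number summary of this instrument. In a small proof-of-concept trial, exploratory effect sizes may be carried into later planning, so a systematic shrinkage is worth removing when removal costs almost nothing.

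The responder wording is a smaller matter. A change of at least 50% without a direction can be programmed in more than one way, and the tabulation is to be done internally by the sponsor.

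**Working it through.** **The plan's own figure.** The documents give no sample size, effect or SD for CeD PRO. The only design figure is for the primary endpoint: 24 subjects (16 and 8), difference 20, SD 17.4, two-sided alpha 0.10, power at least about 80%. Recomputed power is 84.4% (normal) or 82.3% (noncentral t), which is consistent. Only the arm sizes are used below.

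**Week 0 contrast.** Let D0 be the difference between arms in mean baseline score and b the common baseline slope. Because response and covariate are the same score at Week 0, the adjusted contrast with complete data is D0 − b × D0 = (1 − b) × D0. With a pre-dose Week 0 this is chance imbalance, with expectation zero under randomisation.

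**Overall contrast.** Inputs: 17 weekly levels (0 to 16), and equal weighting of weeks. The weighting is an assumption about how SAS fills in the unstated interaction coefficients. With effect d in each of Weeks 1 to 16 and zero at Week 0:

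- overall estimate = (0 + 16d)/17 = 0.941d
- loss = 1/17 = 5.9%

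If the effect varies by week, the same ratio applies to its mean over Weeks 1 to 16. The printed interaction rows carry 18 coefficients per arm, while Weeks 0 to 16 give 17 levels; averaging over 18 would give 1/18 = 5.6%.

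**Simulation.** 16 versus 8 subjects, AR(1) fit by REML, 250 trials per setting. The SD of 10, true effect of −6 and correlations are assumptions, since the documents give none.

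| Correlation assumed | Estimate, Weeks 0–16 | Estimate, Weeks 1–16 | Ratio | Model SE, Weeks 0–16 / 1–16 | Rejection, Weeks 0–16 / 1–16 |
|---|---|---|---|---|---|
| AR(1), 0.7 | −5.638 | −6.002 | 0.939 | 2.249 / 2.361 | 67% / 68% |
| AR(1), 0.9 | −6.168 | −6.565 | 0.940 | 2.716 / 2.867 | 57% / 57% |
| Subject effect + AR(1), 0.5 | −5.404 | −5.743 | 0.941 | 1.716 / 1.848 | 81% / 79% |
| Subject effect + AR(1), 0.8 | −5.827 | −6.200 | 0.940 | 2.114 / 2.270 | 70% / 69% |

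The ratios match 16/17 = 0.941. The model SE falls by 5% to 7% (for example 1 − 2.249/2.361 = 4.7% and 1 − 1.716/1.848 = 7.1%), so rejection rates hardly move. The average Week 0 contrast in these four settings lay between −0.256 and −0.012, against a true later effect of −6. The baseline slope rose by 0.03 to 0.07 when Week 0 was included (for example 0.19 to 0.26).

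**Responder wording.** SAP 8.2.1 defines relative change as post-baseline minus pre-dose, divided by pre-dose, so a positive value is a worsening on this scale. The aberrant-IEL table (SAP 8.6.1) asks for a reduction and the VH:CD table (SAP 8.6.2) for an improvement; the CeD PRO sentence states neither. The ratio is undefined at a baseline of zero. A zero score is possible, because Protocol 9.1, criterion 4, does not require current symptoms in previously treated or steroid-treated subjects.

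**The case against.** The strongest objection is that the SAP never states which days make up Week 0. Days 0 to 112 are 113 = 1 + 16 × 7 days. That fits Day 0 alone followed by 16 full weeks, but also 16 full weeks from Day 0 with Day 112 left as Week 16. On the second reading Week 0 covers Days 0 to 6 and is mostly post-dose. If the covariate were then the Day 0 score, overlap would be partial and 5.9% a ceiling. The ceiling stands, hence the words up to. The escape does not: SAP 8.2.1 has its own rule for weekly scores and the code has its own weekly baseline variable, so the Week 0 score is the covariate under either window. With Days 0 to 6 the covariate would also be partly on treatment, which is a further reason to define the window.

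It is also fair that the endpoint is exploratory, that the SAP says the instrument is not validated in RCD-II, and that the contrasts for Weeks 1 to 16 are touched only through the slope. These points limit the importance of the fault; they do not justify keeping it.

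Some stronger readings are not supported:

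- **Lost power.** Estimate and standard error shrink together.
- **Residual variance distorted by a row with almost no residual.** With one common slope, the Week 0 residual is (1 − b) of the subject's baseline deviation. At the simulated slopes of 0.26 to 0.68 that is 0.74 to 0.32 of it, so not near zero.
- **A 1/113 dilution in the daily model.** Day is continuous there, so nothing averages over 113 days.
- **A breach of the protocol.** Protocol 22.6 and 22.7 name the type of model but not its first time point. GSRS is a sensible template, not proof of departure.
- **A responder table that counts worsening as response.** The sentence leaves the direction open; it does not say that.

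**Conclusion.** The point holds as a minor error in an exploratory analysis. As written, Week 0 is both covariate and response, its contrast measures no treatment effect, and the overall weekly estimate is reduced by up to 5.9%. That size rests on equal week weights, a constant effect over Weeks 1 to 16 (or reading d as their mean) and a Week 0 contrast near zero. The consequence is for the size and meaning of the estimate; the test is practically unchanged. The undirected 50% change is a wording gap and nothing more.

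**What to change.** In SAP 8.7.6:

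- Start the weekly response at k = 1, as in the GSRS model, and delete the Week 0 contrast. Keep the Week 0 score as covariate only, and set the interaction rows to the 16 remaining weeks.
- State which days form Week 0.
- Where the fallback baseline comes from a later week, do not use that week as an outcome for that subject. Moving the start to Week 1 does not cover this case, and the same overlap can arise in the GSRS model.
- Reword the responder tabulation as at least a 50% reduction from baseline, among subjects with a non-zero baseline score.

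The cost is a few characters of code and a few sentences. SAP 8.6.1 lets the SAS code change without an amendment, but the week range in the model equation and the responder sentence are plan text and should be corrected there before unblinding. No data collection changes.

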8.7.7 Assessment of the gluten-free diet (iVYLISA GIP stool test and dietician consultation)

In celiac disease, identification of gluten contamination is essential for the management of the disease and for the successful conduct of clinical trials. Contaminating gluten is a confounding factor in both diagnosis of RCD-II and in the evaluation of a potential therapeutic effect of any experimental medication. Histologic and clinical endpoints are heavily influenced by the presence of gluten in the diet.

Because of that the iVYLISA GIP-S gluten stool test, a gluten assay developed to detect inadvertent gluten consumption by measuring gluten immunogenic peptides (GIP) in feces (Comino et al, 2012), will be used in the CELIM-RCD-002 trial to assist with data interpretation by assessing if the subjects are compliant with the GFD before enrolment and during the study.

The test detects gluten for up to between four and seven days after consumption, and testing will be done every two weeks – subjects should provide a stool sample collected up to 3 days before the visit to the sites, in order to have a good probability of identifying dietary

transgressors to enable correct data interpretation. Testing will be done at a central lab. For the purpose of the study, the test is considered negative when the average amount of gluten of a stool sample is <300 ng GIP/g stool sample.

In addition to the gluten stool test, adherence to the gluten-free diet (GFD) will be assessed periodically (see [Appendix 1](#)) by an expert dietician who will counsel the subjects. The dietician will fill out a questionnaire, provided by the Sponsor, to document the conversation and any detected dietary transgressions. This information may be analysed in an exploratory fashion.

The questionnaire will address the following items:

- Did the subject have nutritional counselling with an expert dietitian during the visit? (Yes/No)
- Was a dietary transgression detected since the last visit? (Yes/No)
- If Yes, please indicate the number of transgressions since the last visit.

Patients will be provided a calendar or similar tool to note their dietary transgressions between visits.

iVYLISA GIP stool test results (positive/negative) will be presented by visit and treatment group as well as listed. Dietician assessment of gluten-free diet (i.e. number of transgressions and counselling with expert dietician) will be tabulated by treatment group and visit as well as listed. The mean numbers of transgressions will also be plotted by visit and treatment group.

ITT analysis set will be used.

8.8 Analysis of safety and tolerability

8.8.1 Adverse events

Adverse events (AEs) and adverse drug reactions (ADRs) reported after administration of the study treatment will be classified by system organ classes (SOC) and preferred terms using the MedDRA dictionary (version 18.1). An ADR is defined as an AE to which the study treatment is assessed to be related by the investigator.

The number and proportion (%) of subjects having each AE or ADR will be given by treatment group. The numbers and proportions will be additionally broken down by severity (mild, moderate, severe) and by the causality (definitely not related, unlikely to be related, possibly related, probably related, definitely related). In addition, the number of events and their proportion (%) of the total number of events will be tabulated. All AEs and SAEs will also be listed.

Additionally, narrative descriptions will be included in the study report for all SAEs and AEs leading to discontinuation of the treatment.

Any symptoms recorded before entry to the study, which remained unchanged or improved, will be followed and evaluated separately from the AEs. If the severity of a symptom increases during the study, the symptom will be considered an AE and it will be reported in the AE section.

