21 ADVERSE EVENTS AND SERIOUS ADVERSE EVENTS

21.1 REPORTING RESPONSIBILITY

The Investigator and study staff are responsible for detecting and recording AEs and SAEs, during scheduled safety evaluations and whenever such information is brought to their attention. This section of the protocol provides definitions and detailed procedures to be followed.

During each visit, the Investigator or qualified designee will assess adverse events using an open question that does not to influence the subject's answers, e.g., "have you noticed any change in your health?"

All AEs occurring after signing of the Informed Consent, and at or before the final visit must be reported regardless of suspected relationship to study drug.

All AEs will be evaluated by the Investigator and intensity (severity) and relationships to study drug will be assessed and recorded.

Any AEs already documented at a previous assessment and designated as ongoing, should be reviewed at subsequent visits as necessary. If these have resolved, the resolution date should be documented. Changes in intensity or frequency of AEs should be recorded as separate events (i.e., a new record started).

AEs and SAEs in possible subjects traveling to study sites from countries other than the study site country will be assessed and managed in the same fashion as those appearing in subjects from the study site countries.

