21.2 DEFINITION OF AN AE

An AE is any untoward medical occurrence (e.g., sign, symptom, disease, syndrome, intercurrent illness) that occurs in a study subject, following the signing of informed consent, regardless of the suspected cause. Only subjects who have been exposed to study drug (active drug or placebo) can experience treatment emergent AEs. Untoward experiences occurring prior to initiation of first administration of study drug are considered non-treatment emergent AEs.

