21.3 SEVERITY

The term of severity is used to describe the intensity of a specific event. The event itself, however, may be of minor medical significance. This is not the same as serious, which is based

on outcome of the event. Seriousness, not intensity, serves as a guide for defining regulatory reporting obligations.

For all AEs, severity will be recorded in the source documents and reported on the appropriate AE eCRF page. There are 3 levels of severity, defined as follows:

Mild: Noticeable, but does not disrupt normal daily activity

Moderate: Sufficient to reduce or disturb normal daily activity

Severe: Incapacitating, significantly interferes with or prevents normal daily activity

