22.8 SAFETY ANALYSES

22.8.1 Adverse Events

All AEs will be coded using MedDRA. The AEs will be summarized by system organ class (SOC), preferred term and separately by causality and severity.

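### One continuing adverse event can be counted several times: Protocol 21.1 splits it into separate records and SAP 8.8.1 counts events without joining them or taking the worst severity

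*SAP*

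**What the plan says.** **How AEs are recorded.** Protocol section 21.1: "Changes in intensity or frequency of AEs should be recorded as separate events (i.e., a new record started"). The rule does not depend on direction, so improvement opens a record as well as worsening, and a change in frequency does so even at the same grade. Each record carries a severity: "There are 3 levels of severity, defined as follows" (Protocol 21.3).

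**How AEs are counted.** SAP section 8.8.1 describes two kinds of count. The first is by subject: "The number and proportion (%) of subjects having each AE or ADR will be given by treatment group". It continues: "The numbers and proportions will be additionally broken down by severity (mild, moderate, severe") and by causality. The second is by event: "the number of events and their proportion (%) of the total number of events will be tabulated". Protocol 22.8.1 says only: "The AEs will be summarized by system organ class (SOC), preferred term and separately by causality and severity". Neither section says what one event is for counting purposes.

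**Which AEs are selected.** SAP 8.8.1 takes "Adverse events (AEs) and adverse drug reactions (ADRs) reported after administration of the study treatment". Protocol 21.2 draws the line by occurrence: "Untoward experiences occurring prior to initiation of first administration of study drug are considered non-treatment emergent AEs".

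**The concern.** The recording rule and the counting rule are each clear, but together they give a result that the sponsor probably does not intend. Sites must split one continuing AE into several records, and the protocol calls those records events. The SAP then counts events. A programmer who follows both documents will count a headache that goes from mild to moderate and back to mild as three events.

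The severity tables have a related gap. With no worst-severity rule, a subject with one AE that moved from mild to severe qualifies for both rows, so the rows need not add up to the number of subjects with that AE. The same holds for causality if the relationship is judged differently on the later record.

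Safety and tolerability are the trial's secondary objective. With 16 and 8 subjects planned per arm, a few split records can visibly move an event count or percentage. The event totals would then reflect how often AEs fluctuate as well as how many occurred.

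Selecting AEs by time of report is a separate mismatch. AE collection starts at consent and screening lasts up to 28 days, so AEs from before the first dose can exist, and one first reported after dosing fits the SAP wording while the protocol calls it non-treatment-emergent.

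**Working it through.** The plan gives no AE figure to reproduce. The check is a reading of the two texts, followed by a simple count under stated assumptions.

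**Step 1: is there a joining or worst-severity rule?** I read Protocol 21.1 to 21.9 and 22.8.1, and SAP sections 2, 8.2 and 8.8.1. There is none. The nearest text is Protocol 21.7. It keeps stable chronic conditions and typical fluctuations of the disease under study off the AE page, and asks for a diagnosis instead of its component symptoms. This limits what is entered; it does not join records once an entered AE changes.

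**Step 2: event totals.** Let f be the share of AEs that change and c the mean number of changes in those that do. Each change adds one record, so

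records ÷ true AEs = 1 + f × c,

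that is, 1 plus the mean number of changes per AE. The values of f and c below are assumptions; the documents give neither.

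| f | c = 1 | c = 2 | c = 4 |
|---|---|---|---|
| 10% | 1.10 | 1.20 | 1.40 |
| 25% | 1.25 | 1.50 | 2.00 |
| 50% | 1.50 | 2.00 | 3.00 |

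The percentage of all events shifts too. If preferred term k has n_k true AEs with m_k changes each on average, its tabulated share is n_k(1 + m_k) ÷ Σ n_j(1 + m_j). This equals the true share for every term only if all terms change equally often.

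**Step 3: severity rows, counted by subject.** Assume ten subjects with one AE each, whose worst grades are 6 mild, 3 moderate and 1 severe, and let each AE climb through the grades from mild.

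- Records: 6 × 1 + 3 × 2 + 1 × 3 = 15. If each AE also steps back down: 6 × 1 + 3 × 3 + 1 × 5 = 20.
- Subjects in each row with no worst-severity rule: mild 6 + 3 + 1 = 10; moderate 3 + 1 = 4; severe 1. The rows add up to 15 for 10 subjects, in both patterns.
- Subjects in each row at worst severity: 6, 3 and 1, adding up to 10.

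The severe row is right either way. The lower rows are overfilled.

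**Step 4: what is not affected.** A subject counts once for a preferred term or system organ class however many records exist, so overall subject incidence stands.

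**Step 5: selection.** Side by side, the SAP uses the time of reporting and the protocol the time of occurrence. They differ for an AE that began before the first infusion and was first reported after it. The documents do not show how many there would be.

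**The case against.** Several arguments limit the point.

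- **The protocol itself calls these separate events**, so counting them as events follows its own term. That is true, but then the event table does not count distinct AEs, and the SAP should say so.
- **Severity is broken down by subject.** A reader might infer that the share of severe events is diluted, because each severe AE also adds milder records. The documents do not support that: in SAP 8.8.1 the severity breakdown follows the subject counts, and the event counts come afterwards with no severity split. The duplicate subject rows are what remains.
- **Protocol 21.7 limits the inflation.** Typical disease fluctuations captured by the efficacy assessments need no AE page, so many of the symptoms most likely to wax and wane may never be recorded as AEs. This stands, and it is a reason not to assume a large factor.
- **No bias between arms is shown.** Equal inflation in both arms leaves the ratio of their event counts unchanged, and nothing in the documents points to a difference.
- **AEs that begin before dosing and improve.** A reader might infer that these enter the tables as new events. SAP 8.8.1 evaluates separately those symptoms recorded before study entry that stay unchanged or improve, and Protocol 11.1 treats entry as randomization, so this is largely covered. Nor does the Visit 1 list show that AEs are first asked about after the infusion; it is an unnumbered checklist.
- **The information is not lost.** All AEs are listed, and serious AEs and those leading to discontinuation get narratives. SAP 8.8.1 specifies no test on AEs.
- **A footnote may exist.** SAP Appendix 4 (table templates) is named, but its content is not in the available text and could hold a counting rule.

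**Conclusion.** The point holds as a minor-to-moderate correction to safety reporting. Taken literally, Protocol 21.1 and SAP 8.8.1 count one continuing AE more than once in the event totals if its grade or frequency changes, and allow one subject with one AE to appear in several severity rows. The event total is inflated by 1 plus the mean number of changes per AE. The size cannot be derived from the documents; the factors of 1.10 to 3.00 above rest wholly on assumed values. The conclusion also assumes that no counting rule sits in the table templates.

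Subject incidence by system organ class and preferred term is not affected, and neither is the primary efficacy analysis. No distortion of the comparison between arms has been shown.

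The selection wording is a real mismatch between the SAP and Protocol 21.2 and should be corrected, but no size can be given for it.

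**What to change.** Add three rules to SAP 8.8.1:

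1. Count linked records of one continuous AE (same subject and preferred term, with no resolution between them) as one event, at its worst severity and strongest relationship. Keep the raw records in the listing.
2. In the breakdown tables, count each subject once per system organ class and preferred term at worst severity, and likewise at strongest relationship.
3. Select treatment-emergent AEs by onset or worsening at or after the start of the first infusion, in line with Protocol 21.2.

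If Appendix 4 already holds a counting footnote, move it into the SAP text and check that it agrees.

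The cost is a few sentences and routine derived-data programming; data collection does not change. There are two drawbacks. Event counts will differ from the raw eCRF record counts, and joining contiguous records may occasionally merge distinct events. The listing should therefore show which records were linked.
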